3.2.2. Randomization/Assignment to Investigational Product or Placebo

Subjects will be assigned a subject number at their Screening Visit. Eligible subjects will be randomized at their study visit Day 1 to a blinded treatment code within the randomization schema. To be eligible for randomization, the subject must fulfill the following requirements:

- Meet all study inclusion criteria and none of the exclusion criteria
- Have acceptable Screening clinical laboratory test results
- Have signed the Informed Consent form
- Comply with the study instructions

3.2.3. Subject Re-screening

Subjects are allowed to be re-screened once. Re-screens are limited to subjects who did not meet inclusion/exclusion criteria due to a transient reason. Transient refers to self-limiting and predictably resolving conditions or acute events (e.g., seasonal allergies, common cold, or otitis media), reversible medical conditions that are successfully treated (e.g., anemia successfully treated by infusion), and/or being unable to comply with study procedures due to administrative convenience (e.g., family issues or attending to a private matter).

Subjects who failed any entry criteria in which no further treatment or spontaneous resolution is expected are not allowed to be re-screened.

Any re-screened subject must be re-consented and will be issued a new subject number. All screening procedures and assessments must be performed at re-screen; no results or data may be used from the previous screen.

3.2.4. Unblinding During the Study

The blind may be broken by a qualified physician who is an Investigator in this study in the

event of a medical emergency in which knowledge of the identity of the study medication is critical to the management of the subject's immediate course of treatment. Before breaking the blind, the Investigator should determine that the information is necessary (i.e., that it will alter the subject's immediate course of treatment).

If deemed necessary to break the blind for a study subject, the Samumed Medical Monitor is to be contacted to obtain concurrence. If it is not possible to contact the Medical Monitor beforehand, he or she should be contacted as soon as possible after breaking the blind for a subject. Details regarding the emergency unblinding will be documented in Medidata Balance and medical records. Instructions on how to unblind treatment assignment will be provided to each Investigator and kept within a guidance document at each site. No other site users will have access roles to Balance that will allow treatment assignment unblinding.

Any subject whose blind has been broken will continue their follow-up visits as per protocol.

An interim analysis will be performed after all subjects have completed their Week 26 visit; however clinical study sites and subjects will remain blinded throughout the study. Only the study sponsor will be unblinded at this time.

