4.3. Strategies for Recruitment and Retention

The Investigator is responsible for retention of study subjects at the study site. Specific training regarding retention of study subjects will be provided by the Sponsor to all sites after all subjects have completed the Week 26 visit. This training will include strategies that the sites should

employ to maintain best efforts for subject retention. The Sponsor is responsible for tracking participation to ensure proper retention of study subjects and will work with the site(s) to develop a site-specific action plan if needed.

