9. SAFETY MONITORING AND ADVERSE EVENTS

9.1. Treatment-Emergent Adverse Events (TEAEs)

Data regarding TEAEs will be collected in this study. TEAEs are events that are not present prior to study medication injection or, if present prior to study medication injection, have worsened in severity.

The reporting period for AEs starts after the injection of study medication on Day 1 and ends after the final study visit.

Definition of Adverse Events:

Adverse events in the eCRF will be classified according to the most recent US FDA definitions and in a manner consistent with ICH guidelines. As such the following definitions will be used:

An adverse event (AE) is any unfavorable and unintended sign, symptom, or disease temporally associated with the use of an investigational (medicinal) product (IP) or other protocol-imposed intervention, regardless of attribution. An AE may include intercurrent illnesses or injuries that represent an exacerbation (increase in frequency, severity, or specificity) of preexisting conditions (e.g., worsening of asthma).

The Investigator must report all laboratory results that are BOTH outside the normal range for the laboratory or has a toxicity grade of 1 or greater AND, in the opinion of the Investigator, are clinically significant. If any abnormal, clinically significant laboratory measure is found after informed consent but prior to study medication injection, the subject is to be excluded. If it is found after study medication injection, it should be reported as an AE.

Whenever possible, it is preferable to record a diagnosis as the AE term rather than a series of symptoms relating to a diagnosis. In order to classify AEs and diseases, preferred terms will be assigned by the Sponsor to the original terms entered on the eCRF, using the Medical Dictionary for Regulatory Activities (MedDRA).

The Investigator will assess AEs for severity utilizing the “Guidance for Industry: Toxicity Scale for Healthy Adult and Adolescent Volunteers Enrolled in Preventive Vaccine Trials”. This toxicity scale is presented in [Appendix 2](#). Laboratory values not listed on the toxicity scale will be assessed for severity by the clinical Investigator.

All adverse events that occur during this trial will be considered related to the study treatment.

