10.5.4. Interim Analysis

An interim analysis will be performed after all subjects have completed their Week 26 visit; however clinical study sites and subjects will remain blinded throughout the study. The aim of this interim analysis is to assess safety and efficacy objectives at Weeks 13 and 26. No trial adaptation(s) will be made based upon these results.

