11.2. Study Monitoring

All aspects of the study will be monitored by the Sponsor or the Sponsor's designees with respect to current Good Clinical Practice (GCP) and Standard Operating Procedures (SOPs) for compliance with applicable government regulations. It is the responsibility of the Investigator to provide all study records, including eCRFs and source documents among other records, for review and inspection by the clinical monitor.

All eCRFs will be 100% source verified against corresponding source documentation (e.g.,

office and clinical laboratory records) for each subject. Clinical monitors will periodically evaluate the progress of the study, including the verification of appropriate consent form procedures, review of drug accountability and preparation procedures, adherence to dosing procedures, and the verification of the accuracy and completeness of eCRFs. Clinical monitors will also ensure that all protocol requirements, applicable US FDA regulations, other Regulatory requirements, and the Investigator's obligations are being fulfilled.

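### From the Week 26 interim to Week 52 the sponsor is unblinded, with no stated limit on who or at what level, while it still codes adverse events, monitors the study and tracks retention

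*Protocol*

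**What the plan says.** Protocol 10.5.4 sets the trigger: "An interim analysis will be performed after all subjects have completed their Week 26 visit". Protocol 3.2.4 says who stays blinded, "however clinical study sites and subjects will remain blinded throughout the study", and who does not: "Only the study sponsor will be unblinded at this time". Protocol 10.5.4 adds: "No trial adaptation(s) will be made based upon these results". SAP 5.1 repeats that there will be no adaptation.

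The protocol leaves these tasks with the sponsor after that point:

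- **Retention (4.3).** Training in retention "will be provided by the Sponsor to all sites after all subjects have completed the Week 26 visit", the same milestone that triggers the unblinding. In addition, "The Sponsor is responsible for tracking participation to ensure proper retention of study subjects", and the sponsor works with sites on action plans where needed.
- **Adverse-event coding (9.1).** MedDRA "preferred terms will be assigned by the Sponsor to the original terms entered on the eCRF".
- **Monitoring (11.2).** "All aspects of the study will be monitored by the Sponsor" or by its designees.
- **Medical monitoring (3.2.4, 3.3.4, 4.4).** The sponsor's medical monitor is consulted on emergency unblinding and is told of prohibited therapies and discontinuations.

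The SAP does not narrow the group that is unblinded. Its section 5.1 covers data cleaning, the snapshot and sequestration, but not who may see treatment codes.

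**The concern.** Coding a reported term, raising a query and deciding how hard to pursue a missing visit all involve judgement. If the people doing this can see each subject's arm, those judgements can differ by arm without anyone intending it. The results that could be touched are the cumulative safety summaries, the Week 39 and 52 efficacy results and SF-36. Safety is a secondary objective, and treatment-emergent events are collected to Week 52.

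Since no adaptation follows the interim, the documents give no reason for the coding, query, monitoring or retention roles to hold subject-level codes. The protocol already separates roles in this way elsewhere. Site staff who prepare or inject the product may not perform assessments (3.2.1), and dispensing logs go to a designated unblinded monitor (8.4).

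**Working it through.** The plan states no figure to reproduce here. The check has two parts: which data are still open to influence after unblinding, and how many visits that involves.

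**1. What is and is not exposed**

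| Data | Position at the sponsor's unblinding |
|---|---|
| Primary and secondary efficacy, Weeks 13 and 26 (H1–H21, SAP 8.2.1) | Source verification, queries and Week 26 joint space width measurement are finished first. The data are then sequestered (SAP 5.1) and the analyses are not repeated (SAP 8.3). None of the 21 tests uses later data. |
| Adverse events up to Week 26 | Those available are in the snapshot before unblinding (SAP 5.1). |
| Later adverse events | Reported and graded at blinded sites; preferred terms are then assigned by the unblinded sponsor. They enter the cumulative final report (SAP 7). |
| Week 39 and 52 efficacy | Exploratory (Protocol 2.2, SAP 1.3). For visits after unblinding, collection and querying take place while the sponsor is unblinded. The SAP's multiple imputation is for primary and secondary analyses and its tipping-point analysis for the primary one, so neither covers late dropout. |
| SF-36, all visits | Absent from the interim list (SAP 8.2) and analysed only at the end (SAP 8.3). Verification before unblinding is promised only for data supporting the interim, so even the Week 4 to 26 scores are not expressly covered. |

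**2. How many visits are still due**

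Inputs from the documents: first subject August 2015 and last subject completed April 2017 (Protocol synopsis); visits at 182, 273 and 365 days after injection (Protocol 6.5 to 6.7); 445 subjects.

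Assumptions: even enrolment over E days, no dropout, visits on their nominal day, and a cleaning lag of L days (0 to 60) between the last Week 26 visit and unblinding.

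- Enrolment period: E = (last completion − first enrolment) − 365 days.
- Unblinding falls on day E + 182 + L.
- Share of Week 52 visits still due = (365 − 182 − L)/E = (183 − L)/E.
- Share of Week 39 visits still due = (273 − 182 − L)/E = (91 − L)/E.

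Mid-case, 15 August 2015 to 15 April 2017: 609 − 365 gives E = 244 days, about 8 months. With L = 0:

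- Week 52: 183/244 = 75%, about 334 of 445 subjects.
- Week 39: 91/244 = 37%, about 166 of 445 subjects.

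Range over dates within the stated months and over the lag:

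| E (days) | L (days) | Week 52 still due | Week 39 still due |
|---|---|---|---|
| 273 | 0 | 67% | 33% |
| 273 | 60 | 123/273 = 45% | 31/273 = 11% |
| 244 | 0 | 75% | 37% |
| 244 | 60 | 50% | 13% |
| 214 | 0 | 183/214 = 86% | 91/214 = 43% |
| 214 | 60 | 57% | 14% |

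The sponsor is unblinded for (183 − L) days before the last subject's Week 52 visit, which is 123 to 183 days, or about 4 to 6 months.

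**The case against.** The strongest reply is that the data that matter most are already safe. Subjects complete WOMAC, Patient Global and SF-36 themselves, Physician Global is completed at the blinded site, and radiographs go to an independent radiologist. The efficacy tests in the hierarchy are complete, cleaned and sequestered beforehand. All of this stands.

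The retention route is also weak. Protocol 4.3 makes the investigator responsible for retention at the site, the training goes to all sites, and action plans are specific to sites, not to subjects. Randomization is 1:1:1:1 in blocks of 8 within site, which puts two subjects per arm in each block. Site-level effort therefore reaches all arms about equally. For effort to differ by arm, the sponsor would have to direct a blinded site to particular subjects, and nothing in the documents provides for that.

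Monitoring may be delegated, and 100% source verification leaves no room for selective coverage. For safety, detection and grading happen at blinded sites, every event is treated as related, and Protocol 10.5.3 plans no formal tests.

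These points limit the concern but do not remove it. Preferred-term assignment, queries and conduct decisions on later data remain with an organisation that is allowed to know treatment.

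Two stronger readings are tempting. A reader might infer that everyone at the sponsor will see subject-level codes. That comes only from silence, since the text does not say who is unblinded or at what level. A reader might also infer that the double blind no longer protects later outcomes. The protocol says the opposite for subjects and sites, and what is lost is the sponsor-level blind alone.

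**Conclusion.** The point holds in limited form. Protocol 3.2.4 permits sponsor unblinding at the interim without naming a group or level, and the sponsor keeps coding, monitoring and retention tasks to Week 52. The exposure covers coding and querying of later adverse events, exploratory Week 39 and 52 efficacy, and SF-36. The primary and secondary efficacy results at Weeks 13 and 26 are not affected.

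Under even enrolment, 45–86% of Week 52 visits and 11–43% of Week 39 visits are still to come at unblinding. These shares depend on the assumed dates, enrolment pattern and cleaning lag. They say nothing about the size or direction of any bias, which the documents do not allow one to estimate. This is a low-priority improvement, worth making because it is cheap.

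**What to change.** In Protocol 3.2.4:

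- Limit subject-level unblinding at the interim to a statistics and programming group with no site-contact, coding or query role.
- Keep the medical monitor (apart from emergency unblinding), clinical operations, data management and adverse-event coders blinded to subject-level treatment until final database lock.
- Allow wider access within the sponsor to group-level results only.

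The cost is protocol wording and access control. No sample size, test or visit changes. The downside is that sponsor operations staff see only summaries until Week 52.

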3.3. Investigational Product

3.3.1. Rationale for Dosages and Dosing Regimen

A phase 1 clinical trial was conducted to assess the safety, tolerability, pharmacokinetics (PK), and pharmacodynamics (PD) of a SM04690 formulation at 3 different dose-level concentrations (0.03, 0.07, and 0.23 mg per 2 mL injection) injected into the intra-articular space of the OA-affected target knee. The initial dose level of SM04690 (0.03 mg) was based on the mammalian species most sensitive to SM04690 in 8-week toxicology studies (the approximate residence time of the drug) in accordance with US Food and Drug Administration (FDA) guidelines. Preclinical studies to date have not demonstrated toxicity or systemic exposure at the biologically efficacious dose, so doses were selected that bracketed the projected biologically efficacious dose based on preclinical studies, hence resulting in the escalation sequence of 0.03, 0.07, and 0.23 mg per 2 mL injection.

As of 07 July 2015, 61 subjects have been enrolled in 3 ascending dose cohorts of approximately 20 subjects per cohort. Per protocol, data from cohort 1 and 2 were unblinded following the safety review of all subjects enrolled in the cohort (observed for a minimum of 12 weeks). Cohort 3 data remains blinded.

A total of 28/61 subjects have reported 68 treatment emergent adverse events (TEAEs) with 35 preferred terms. The system organ class (SOC) most reported was 'Musculoskeletal and connective tissue disorders' with 11/61 subjects reporting 19 TEAEs of 5 preferred terms.

As of 07 July 2015, following dosing in all three cohorts, there have been two dose-limiting toxicities (DLTs) and 1 serious adverse event (SAE) reported on the trial. A DLT of increased knee pain was reported and met the DLT criteria of increased pain at the target joint of greater than 30 mm increase on the pain VAS; this DLT was due to a procedural error and considered unrelated to study drug. A DLT of tachycardia paroxysmal was also reported and met the DLT criteria of an AE deemed by the investigator to be a severe or serious AE. This DLT also met

3.3.2. Dosages and Dosing Regimen

SM04690 will be administered in the following dosage strengths:

- SM04690 0.03 mg in 2 mL Injectable Suspension
- SM04690 0.07 mg in 2 mL Injectable Suspension
- SM04690 0.23 mg in 2 mL Injectable Suspension
- SM04690 0 mg; placebo (PBS) injection only

Each subject will be randomly assigned to a dose at Study Visit Day 1. The injectable investigational product or the placebo (PBS) is to be administered as a 1-time single injection into the target knee joint. Only 1 knee will be treated for each subject in this study.

Only topical anesthetic (absolutely no invasive anesthetic) is allowed for the study injections. Anesthetic is also not allowed to be combined with the study medication for injection.

3.3.3. Dose Modifications

No modification in the specified dose concentration or the volume (2 mL) of the study medication injected into the target knee joint will be allowed.

3.3.4. Prior and Concomitant Medications and Procedures

Prior medications are defined as medications that were taken within 30 days prior to study injection on Day 1. Concomitant medications are defined as medications taken any time after study injection on Day 1 until follow-up visit Week 52 (EOS)/Early Termination. All prior and new or modified concomitant therapy used during the study must be recorded on the "Prior and Concomitant Medications" page of the eCRF.

Procedures that are ongoing, new, or modified at or post-Day 1 must be recorded on the "Procedures and Non-Drug Therapies" page of the eCRF.

Any new or modified concomitant therapy must be considered to determine if it is related to an adverse event (AE).

Subjects will be encouraged to remain on a stable dose of any allowed medications throughout the study. The use of aspirin (325 mg/day) for thrombosis prophylaxis is permitted.

Prohibited Concomitant Medications and Procedures:

- Subjects must not take any pain medication or medications/supplements for the treatment of OA within 24 hours prior to their scheduled visit, excluding the Screening Visit. This includes both OTC and prescription pain medications.
- Subjects must not participate in a formalized in-office and/or supervised OA disease program (e.g., a prescribed patient education program, physiotherapy, etc.) within 24 hours prior to their scheduled visit, excluding the Screening Visit.
- Intra-articular injection of steroids (glucocorticoids/corticosteroids), hyaluronic acid derivatives, or other agents with therapeutic intent into either knee is prohibited while the study subject is on study; intra-articular injection of steroids, hyaluronic acid derivatives, or other therapeutic agents into joints other than the knee are allowed.
- The following medications are prohibited while the subject is on study:
 - Opioids, both oral (e.g., tramadol) or transdermal (e.g., fentanyl patches) formulations
 - Centrally acting analgesics (e.g., duloxetine)
 - Glucocorticoids (also referred to as steroids or corticosteroids such as methylprednisolone,) administered by any route, with exception of inhaled, intranasal or ophthalmic application, or intra-articular injection of a non-knee joint.
- Electrotherapy and acupuncture for knee OA are prohibited while the subject is on study.
- Chiropractic adjustments of the knee are prohibited while the subject is on the study.
- Planned or elective surgery, including arthroscopy, is prohibited while the subject is on the study.

At each visit, excluding the Screening Visit, the study coordinator will ask the subject to confirm that no pain medications and medications/supplements for the treatment of OA were taken within the last 24 hours. The Investigator should notify the Samumed Medical Monitor immediately if any prohibited therapies are required to ensure subject safety.

3.4. Duration of Subject Participation

The duration of study participation for each subject is anticipated to be up to 55 weeks. This duration includes the Screening Visit during a screening period of up to 21 days, a 1-day treatment period occurring at Day 1, and a 52-week follow-up period.

3.5. Procedures for Monitoring Subject Compliance

Subjects will return to the clinic for scheduled visits as specified in [Appendix 1](#). Subjects who do not comply with the visit schedule may be discontinued from the study.

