4.4. Procedures for Subject Discontinuation from the Study

As the study treatment requires only a single injection, best efforts will be made to encourage subjects to attend all follow-up visits. Nevertheless, subjects will be informed that they are free to withdraw from the study at any time and for any reason.

The Investigator may remove a subject from the study if, in the Investigator's opinion, it is not in the best interest of the subject to continue in the study; refer to [Section 7](#) for further details. Notification of discontinuation will immediately be made to the Sponsor's medical monitor. In case of premature discontinuation of study participation, efforts will be made to perform all final study day [Week 52 (EOS)/Early Termination] assessments within 14 days of subject discontinuation. The date the subject is withdrawn from the study and the reason for discontinuation will be recorded on the subject's case report form (CRF).

The study may be discontinued at the discretion of the Investigator or the Sponsor.

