7. PREMATURE DISCONTINUATION FROM STUDY

As the study treatment requires only a single injection, best efforts will be made to encourage subjects to attend all follow-up visits. A premature discontinuation from study will occur when a subject who signed informed consent ceases participation in this study, regardless of circumstances, prior to completion of the defined study period. Subjects can be prematurely discontinued from the study for one of the following reasons:

- Death
- Lost to follow-up after a minimum of 2 attempts have been made to contact the subject, including sending a registered letter
- Subject withdraws consent

The reason for the discontinuation should be recorded on the eCRF. The Investigator or designee must complete all applicable eCRF pages for subjects who discontinue from the study prematurely. Week 52 (EOS)/Early Termination procedures should be conducted within 14 days of discontinuation for any subject who discontinues after study injection on Day 1.

The principal Investigator and the Institutional Review Board/Ethics Committee (IRB/EC) reserve the right to prematurely terminate the study in the interest of subject safety and welfare. The Sponsor reserves the right to prematurely terminate the study at any time for administrative reasons.

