6.4. Protocol Deviations

For SM04690-OA-02, a protocol deviation is defined as any change, divergence or departure from the study design or procedures of a research protocol that is under the Investigator's control and that has not been approved by the site's Institutional Review Board.

Deviations are summarized into one of the following categories:

- Those who were randomized to the study even though they did not satisfy the eligibility criteria
- Those who developed withdrawal criteria during the study but were not withdrawn
- Those who received the wrong treatment or incorrect dose
- Those who received an excluded concomitant treatment
- Those who missed or received an incorrect protocol procedure

Deviations are categorized as major or minor.

- A major deviation is defined as a divergence from the protocol that materially (a) reduces the quality or completeness of the data, (b) makes the informed consent inaccurate, or (c) impacts a subject's safety, rights or welfare.
- A minor deviation is defined as a divergence from the protocol that deviates from the procedures and guidelines outlined in the protocol, but is not classified as a major deviation (i.e. the deviation does not materially (a) reduce the quality or completeness of the data, (b) make the informed consent inaccurate, or (c) impact a subject's safety, rights or welfare).

Protocol deviations will be summarized by site, category and classification, and listed for each subject.

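### Protocol 3.5 allows removal from the study for visit non-compliance, a ground missing from the Section 7 list; after a single injection this mainly ends follow-up and adds avoidable missing data, chiefly from Week 26 on

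*Protocol*

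**What the plan says.** Protocol 3.5, on visit compliance: "Subjects who do not comply with the visit schedule may be discontinued from the study". It sets no threshold and does not name who decides.

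Protocol 7: "Subjects can be prematurely discontinued from the study for one of the following reasons". Three items follow: death; "Lost to follow-up after a minimum of 2 attempts have been made to contact the subject, including sending a registered letter"; and "Subject withdraws consent". There is no entry for non-compliance and no residual category. The same section opens with the retention aim: "As the study treatment requires only a single injection, best efforts will be made to encourage subjects to attend all follow-up visits". Section 4.4 repeats that aim.

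Protocol 4.4 adds another ground. "The Investigator may remove a subject from the study if", in that person's opinion, "it is not in the best interest of the subject to continue in the study". It points to Section 7 for more detail, but the Section 7 list does not include this ground.

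SAP 6.4 has a deviation category "Those who developed withdrawal criteria during the study but were not withdrawn". Protocol 3.5, 4.4 and 7 do not use the term withdrawal criteria, so it is unclear which of their grounds the category covers.

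On the analysis side:
- **SAP 5.4** assigns early-termination data to a visit only if they fall in that visit's window. Anything else is missing.
- **SAP 5.2** uses multiple imputation under MAR for the primary and secondary analyses, from the outcome's baseline and treatment group, separately for each timepoint.
- **SAP 5.2.1** limits the tipping-point analysis to the primary analysis, for dose groups already significant.

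**The concern.** Removal for non-compliance usually serves to stop a treatment that cannot be given safely or as planned. Here dosing is complete on Day 1. Removing a subject who came late or missed a visit withdraws nothing from that subject, but it gives up the remaining scheduled assessments. Efficacy is analysed on all randomized subjects, so those assessments still have to be accounted for, by imputation.

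The imputation cannot recover much. A Week 4 or Week 13 score does not inform a later missing value, because each timepoint is imputed separately from baseline and group. If attendance depended on how the knee was doing, MAR imputation would give removed subjects roughly the average course of their arm, and the treatment contrast could move in either direction.

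The rules are also hard to apply uniformly. One site could remove a subject under Section 3.5 while another keeps a similar subject under Section 7. If Section 3.5 counts as a withdrawal criterion, SAP 6.4 could record the retained subject as the deviation.

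**Working it through.** **1. The discontinuation rules side by side**

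| Place | Ground | In the Section 7 list? |
|---|---|---|
| Protocol 3.5 | Visit non-compliance | No |
| Protocol 4.4 | Investigator's judgement of best interest | No |
| Protocol 7 | Death; loss to follow-up; consent withdrawal | Yes |
| SAP 6.4 | Withdrawal criteria, not defined | Cannot be matched |

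A missed visit alone is not loss to follow-up, because Section 7 requires at least two contact attempts including a registered letter. Section 3.5 therefore adds a ground. Section 3.2.4, by contrast, keeps even a subject whose blind was broken in scheduled follow-up.

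**2. Which visits are exposed**

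The only scheduled visit between injection and Week 13 is Week 4. A subject who misses Week 13 itself has no Week 13 value whether or not removed afterwards. So only removal before Week 13 can add missing data to the primary endpoint. Removal at or after Week 13 affects Weeks 26, 39 and 52. In the SAP 8.2.1 hierarchy, H6, H7, H9 and H13 to H21 are Week 26 tests: 3 + 9 = 12 of 21.

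**3. Whether the early-termination visit fills the gap**

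Assume removal as soon as a visit window closes. The early-termination visit is due within 14 days.
- Week 4 missed: window closes 28 + 3 = 31 days after injection; early-termination visit by day 31 + 14 = 45. The Week 13 window is days 88 to 94.
- Week 13 missed: window closes at 94; early-termination visit by day 94 + 14 = 108. The Week 26 window is days 172 to 182.

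In both cases the data fall in no later window, and SAP 5.4 treats the later visit as missing. Later removal could land in a window; the protocol does not fix the timing.

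**4. Illustrative size**

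Neither document gives a rate of removal for non-compliance, so there is no plan figure to reproduce. The rates and the outcome of removed subjects below are assumptions.

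Inputs from SAP 2.1, on the 0–20 scale: active change -5.8, placebo change -3.5. SAP 5.2.1 rescales -3.5 to -8.75, a factor of 2.5. On the 0–50 scale:
- active: 5.8 × 2.5 = 14.5
- placebo: 3.5 × 2.5 = 8.75
- planned difference: 14.5 - 8.75 = 5.75

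SAP 2.1 ties these values to no visit; they stand in for whichever visit follows removal.

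If removed subjects would have had no improvement but are imputed near their own arm's mean, the shift in favour of active is q_A × 14.5 - q_P × 8.75, where q is the share removed.

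| Active removed | Placebo removed | Shift in favour of active |
|---|---|---|
| 5% | 2% | 0.725 - 0.175 = 0.55 |
| 2% | 5% | 0.290 - 0.4375 = -0.15 |
| 5% | 5% | 0.725 - 0.4375 = 0.29 |

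The last row is not zero because no improvement is a larger shortfall on active than on placebo. If the shortfall k is the same in both arms, the shift is (q_A - q_P) × k, which is zero at equal rates.

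With 445 / 4 = 111.25 per arm, 5% and 2% are about 6 and 2 subjects. The planning standard error is 2.5 × 4 × √(1 - 0.1²) × √(2 / 111.25) = 1.33 points. A shift of 0.55 is 0.55 / 5.75 = 10% of the planned difference and 0.55 / 1.33 = 0.41 standard errors.

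**The case against.** The strongest reply is that Section 3.5 is a residual permission. It obliges nobody to remove anyone, and it names no actor. Sections 4.4 and 7 aim for full follow-up, and Section 4.3 makes the investigator responsible for retention and has the sponsor track participation, with site action plans where needed. A discontinued subject still has a full early-termination visit. The tipping-point analysis probes departures from MAR. Section 7 does not say that its list is exclusive.

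Much of this stands, and it is why the point is minor. It does not remove the conflict. A permission that is never meant to be used can be deleted, and a list that is not exhaustive should say so. The retention training in Section 4.3 comes only after all subjects have completed Week 26, which is after every visit in the hierarchy. The early-termination visit rarely lands in a later window if removal is prompt, and the tipping-point analysis does not reach Week 26.

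A reader might infer more than the documents support, in three ways:
- **That the rule creates outcome-related missing data.** Nothing in either document shows how often it would be used or that its use would depend on outcome. That link is plausible and no more.
- **That the Week 13 analysis is broadly at risk.** Only removal before Week 13 can affect it.
- **That the bias has one known size and direction.** Applying the placebo mean to both arms would give a single figure, but imputation is by group, and the sign depends on which arm loses more subjects.

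**Conclusion.** The inconsistency is certain on the text: Section 3.5 allows a removal that the Section 7 list does not contain and that runs against the protocol's retention aim. That such removal costs follow-up data without stopping any treatment follows from the single-injection design.

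The effect on results is conditional. Under the assumed rates of 2% and 5%, with no improvement in those removed, the shift runs from about -0.15 to 0.55 points, and it is about zero where rates and shortfall are equal across arms. These are illustrations, not estimates. For the secondary endpoints at Week 26 there is no planned analysis of departures from MAR that would reveal such a shift. Severity is low; the case for acting is that the correction is nearly free.

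**What to change.** Replace the sentence in Protocol 3.5 with: *Missed or out-of-window visits are recorded as protocol deviations; subjects remain in follow-up for all later visits unless discontinued for a reason listed in Section 7.* SAP 6.4 already has a deviation category for missed procedures, and the per-protocol set already deals with non-compliers, so the analysis loses nothing.

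In the same amendment, reconcile the investigator-judgement ground in Section 4.4 with the Section 7 list. Whether that ground belongs in the list is for the sponsor to decide. Then either define the withdrawal criteria that SAP 6.4 refers to, by pointing to the reconciled list, or delete that category.

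The cost is a wording change and some extra effort by sites to chase late visits. Sample size, testing order and the primary model are unchanged.
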